3.2. Rationale

Developers of software often design without properly understanding the needs of the ultimate users. They solve non-existent problems or do not take the context of users into account. Research is therefore vital to ensure a patient perspective is taken into account from an early stage. Interviews provide a solid way to obtain a deep understanding. Questionnaires help ensure it is widely applicable and so generalisable to a wider population.

There has been an open dialogue with PPI groups from the outset of the project. Draft questionnaires and semi-structured interviews were sent to members of the Rheumatoid Arthritis PPI group, and amended according to feedback. Practice interviews were conducted with volunteers to sense-check and time interviews, with modifications made based on patient feedback.

3.3. Risks / benefits

The study is non-interventional and thus the risks to participants are low. They can withdraw from the study at any point if they find the information being sought is too intrusive.

The main potential risk is of patients' collected data from (security) and appropriate management and oversight of this dataset. Personal data will be stored in line with GCP guidelines to protect patient confidentiality. There may be no direct benefit immediately to patients for participation in the AtT-RA study. However, in the medium to long term it will shape the development of technology supported care used within the department, which may improve patient's understanding and control of their disease.

4. Study objectives

4.1. Primary objective

The overarching objective is to define the main opportunities and challenges to technology supported RA care for patients and clinicians.

4.2. Secondary objective

1. Do the perceived opportunities and challenges vary according to patient demographics e.g. disease activity, disease duration, patient age?
2. What are the challenges of living with Rheumatoid Arthritis? (This will include issues around everyday life, flares, pain, medication and appointments from a patient perspective.)
3. Do the perceived opportunities and challenges vary according to clinician demographics e.g. age, subspeciality?
4. Are there significant differences in patient and clinician expectations for health technology assessed parameters?
5. Have the perceived opportunities and challenges changed since the rapid institution of remote care due to the Covid-19 pandemic?

4.3. Primary endpoint

Thematic Analysis will be used to code emerging themes from patient and clinician interviews and questionnaire responses in order to define the main opportunities and barriers to technology supported care.

5. Study population

Patients with a diagnosis of Rheumatoid Arthritis who are over the age of 18 will be eligible to participate.

Surveys will be distributed to patients attending for outpatient Rheumatology appointments at Mile End hospital, London. Outpatient clinic lists will be screened for appropriate patients, who will be approached whilst waiting for their clinic appointments. Patient interviews will also take place at the hospital. Patients visiting the Rheumatology Department at Mile End Hospital will be recruited while they wait for appointments, and be invited to an interview either on site or remotely, at a later date.

Clinicians eligible will include any with >1 year speciality experience in managing rheumatoid arthritis patients including consultants, registrars, specialist nurses and Allied Health Professionals.

Clinicians across several Rheumatology Centres within the geographical region will be approached by a Rheumatology clinical fellow and asked to participate. Interviews will take place at a location convenient to the interviewee. Clinician questionnaires will be disseminated and administered electronically, via regional and national mailing lists.

5.1. Inclusion criteria

Patients

- Able and willing to give informed consent
- Diagnosis of Rheumatoid Arthritis (made by a Rheumatologist)
- 18 years old or more
- Sufficient English language ability to answer interview questions

Clinicians

- Specialising in Rheumatology
- >1 year speciality experience

Covid-19 sub-study:

- Patients and Clinicians who previously participated in an interview as part of the AtTRA study

5.2. Exclusion criteria

Patients:

- Unwilling or unable to give consent
- Inability to understand written and/ or verbal English (there may be some assistance from a research assistant for Bengali speakers completing the survey; however for the interview there is no translation assistance)

Clinicians:

- Unwilling or unable to give consent
- < 1 year experience in Rheumatology as a specialism
- No longer practicing Rheumatology
- Clinicians working within Rheumatology whom do not routinely look after patients with Rheumatoid Arthritis.

Covid-19 sub-study:

- Patients and Clinicians who did not participate in an interview as part of the AtTRA study

Study design

This is a cross-sectional, mixed methods study, with four parallel arms: Patient questionnaire; Patient interview; Clinician questionnaire and Clinician Interview. Thus the study has both qualitative and quantitative aspects.

Both patient and clinician interviews are Semi-structured. They have been developed by a team of researchers from both EECS and EMR. The interview is structured with 'top' questions, which are open and broad, with sub-questions on important issues to be broached if the interviewee does not volunteer this information when asked the initial 'top' question. A single researcher from EECS will conduct patient interviews, and a single researcher from EMR will conduct clinician interviews, in order to maintain consistency. Interviews will be audio recorded and transcribed by an external transcription service (Bristol Transcription Services) previously used by EECS.

Patient and Clinician questionnaires have been developed by a team of researchers from both EECS and EMR. Patient questionnaires will be paper based with the option for postal return. Clinician questionnaires will be administered electronically.

Patients and Clinicians who participated in an interview will be contacted via letter or email and invited to participate in a brief follow up e-questionnaire (via SurveyMonkey™) regarding how the changes in care due to Covid-19 have impacted their beliefs about the use of technology to support care.

6. Study procedures

Informed Consent

Participants will be asked if they wish to participate in the study following review of a detailed patient information sheet (PIS). Consent will be implied by the decision to complete and return the questionnaire.

For interviews, consent will be obtained by the researcher conducting the interview. A written information sheet will be provided, with a separate consent form. Interviews will be conducted on a separate date from recruitment, so patients will have a minimum of 24 hours to decide if they wish to participate.

For Clinicians, information regarding the study will be circulated via email, including a detailed participant information sheet. A link to the online questionnaire (hosted by Survey Monkey™) will be provided, and the decision to complete the questionnaire will be taken as their consent to participate. Those who express willingness to participate in the interview study will be contacted and written consent taken at the time of interview.

Patients and clinicians who participated in the interview arm of the study will be contacted via email or letter to invite them to participate in a short electronic survey (via SurveyMonkey™) regarding how the changes in care during the Covid-19 pandemic have impacted their beliefs about the use of technology to support care. Completion of the electronic questionnaire will be considered as sufficient consent to participate.

Screening and Recruitment

Patients:

Patients will be identified via outpatient clinics at Mile End Hospital and following discussion with a member of the study team will be provided with a patient information sheet. Patients will be asked to complete a questionnaire and post to return, and if participating in the interview a follow-up visit will be booked to arrange an interview at a convenient time. Patients may agree to participate in either or both arms of the patient study (i.e. questionnaire, interview, or both). Following completion of the interview the patients will have no further issues.

Clinicians:

Clinician e-questionnaires will be disseminated through the contacts of a Rheumatology Clinical Research fellow. Regional and National Rheumatology e-mailing lists will be asked to distribute the questionnaire, including North and South London and KSS (Kings Surrey Sussex) Registrar mailing lists, and the British Society of Rheumatology (BRITs) mailing list.

Clinicians will be recruited for interview via the contacts of a Rheumatology Clinical Research Fellow. A “snowball” sampling method will be employed, so that those who have been interviewed will recommend other potential participants in the study. Potential sites which will be approached include Whipps Cross Hospital, University College Hospital, Homerton Hospital, and Northwick Park Hospital.

Procedures for Collecting Data:

Data will be collected using an ethically approved questionnaire and/or semi-structured interview designed to capture patient’s experiences around the following aspects of RA care:

- Living with Rheumatoid Arthritis
- Managing Flares
- Medication management, monitoring, and adverse effects
- Accessibility of Care and clinic appointments
- Perceived Opportunities and Barriers of technology
- Current technology usage

Paper Questionnaire: The questionnaire itself will act as the source data. The questionnaire will have the patient’s unique study number and initials to identify it but no other patient identifiable information. Clinical information including disease duration, up to date disease activity measures,

comorbidities and medication history will be obtained from the patient record and recorded on a separate record sheet labelled with the patient's unique study number.

Online Questionnaire: The online tool SurveyMonkey™ will be used to distribute and collect data for clinical questionnaires. The questionnaire will have the participant's email address, initials and place of work; but no other identifiable information.

Semi-structured interviews: Will be anonymously recorded and transcribed by an external transcription service previously used by the EECS team. Transcriptions will be analysed and coded at EECS. Once analysed the transcripts will be returned to the site file, stored within a secure locked room in the Department of Experimental Medicine. Participants in semi-structured interviews, who have not participated in the questionnaire arm of the study, will also complete an abridged questionnaire to establish current technology usage and demographics. Clinical information including disease duration, up to date disease activity measures, comorbidities and medication history will be obtained from the patient record and recorded on a separate record sheet labelled with the patient's unique study number.

Participant Withdrawal:

Participants may choose to withdraw from the study at any time.

End of Study Definition:

Interview studies will end when researchers agree that 'meaning saturation' has been reached; i.e. that further interviews will not add any further new information. Questionnaire studies will end when the specified target numbers have been reached.

7. Statistical considerations

Due to the study type there is no statistical powering for the patient population. Although the majority of the study is qualitative, analysis of the quantitative aspects of the questionnaires will be planned with the support of the Experimental Medicine and Rheumatology Statistician to ensure appropriate statistical methods are used in any and all analyses

7.1. Sample size

Patient questionnaire:

100

This target sample size has been set based on the sample size of other similar studies(6).

Clinician questionnaire:

40

This target sample size has been set pragmatically, based upon anticipated responses.

Patient interview:

15-25 participants.

The interviews will be analysed using thematic analysis, which advises stopping data collection when no new information is being gathered. Based upon the literature, “meaning saturation”, when researchers have a full understanding of all aspects of the topic tends to occur between 16-24 interviews⁽⁷⁾.

Clinician interview:

10-15 participants.

As above, the interviews will be analysed using thematic analysis. However, in this case a smaller sample size has been chosen, as the pool of potential participants is smaller. Additionally, we anticipate a smaller number of interviews to be required to reach “meaning saturation” as the interviews will be conducted by a Rheumatology clinical research fellow, and knowledge of the researcher has been demonstrated to reduce the required sample size⁽⁸⁾.

Covid-19 sub-study:

15-25 participants (Patients and Clinicians combined). This target sample size has been set based upon an anticipated $\approx 50\%$ response from previously interviewed participants

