	
understand the day-to-day challenges of living with and managing Rheumatoid Arthritis, in order to design technology which meets the needs of the target users; and the expectations patients and clinicians hold for intelligent mobile technology. This understanding will be used in the short term to improve existing apps and in the longer term as a basis for how next generation mobile health technology could provide support for those directly involved in Rheumatoid Arthritis care.
 
Potential opportunities for support of patients include:
 
 • Helping patients improve quality of life • Improving clinical outcomes by achieving tighter disease control • Supporting patients' clinical decision making • Supporting patient-clinician communication • Reducing the need for direct patient-clinician contact • Patient-patient support • Educating patients • Supporting behavioural change / attitudes to the disease / disease acceptance 
The aim is to determine what, if any, contextual and cultural factors exist around the clinical pathway activities (eg around tapering, attitudes to flares, etc).
 
A Covid-19 questionnaire sub-study has been added to understand how the changes in care instituted during the pandemic may have influenced interview participants' opinions on the use of technology to support care.

Number of participants
	
This is an unpowered study so patient numbers are estimates based upon the literature.
 
Patient Questionnaire 100
 
Patient Semi-Structured Interview 15-25
 
Clinician Questionnaire 40
 
Clinician Semi-Structured interview 10-15
 
Covid-19 sub-study 15-25
 
Total 180-210

Inclusion and exclusion criteria
	
Patients Inclusion: >18 years old, no upper limit on the age range. Rheumatoid Arthritis, diagnosed by a Rheumatologist.

	
Comprehension of Patient Information Sheet and Consent.
 
Patients Exclusion: No formal diagnosis of Rheumatoid Arthritis. Insufficient English Language capability to complete the questionnaire or interview.
 
Clinicians: Doctors, Nurses or Allied Health Professionals Specialising in Rheumatology care for 1 year or more.

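### The Covid-19 sub-study has one combined target for patients and clinicians and appears to end on that count, which suits a closed pool poorly; the target also does not follow from the stated 50% response

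*Protocol*

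**What the plan says.** Protocol section 7.1 gives patients and clinicians their own targets in the four main arms: 100 and 40 for the questionnaires, 15-25 and 10-15 for the interviews. Only the Covid-19 sub-study has a joint figure, "15-25 participants (Patients and Clinicians combined", resting on an anticipated rate of about 50% "response from previously interviewed participants". No minimum per group is given.

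Entry is restricted in section 5.1 to "Patients and Clinicians who previously participated in an interview as part of the AtTRA study", and section 5.2 excludes everyone else. The Study design text says that these people will be "invited to participate in a brief follow up e-questionnaire". The synopsis (Methodology) adds that patients are approached by letter and clinicians by email.

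The End of Study Definition in section 6 reads: "Questionnaire studies will end when the specified target numbers have been reached". No other end rule covers the sub-study.

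The sub-study serves the fifth secondary objective in section 4.2: "Have the perceived opportunities and challenges changed since the rapid institution of remote care due to the Covid-19 pandemic". That objective names neither group. Section 7.2 plans mainly descriptive statistics for the questionnaires and says nothing specific about this one.

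**The concern.** A count-based end rule makes sense where recruitment could continue indefinitely. Here the possible respondents are a fixed list of at most 40 people. Once they have been invited, closing at a number gains nothing: replies still to come are lost, and those already in come from whichever group answers sooner. The two groups are invited by different routes, and patients must go from a paper letter to an online form, so equal speed or equal response cannot be taken for granted. That is an inference; the protocol gives no response rate by group.

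With no minimum per group, the target could be met while one group is thinly represented, and nothing in the protocol would flag a shortfall. Patients receive remote care and clinicians deliver it, and the protocol otherwise treats their views as distinct: the first and third secondary objectives take them separately and the fourth compares them. At stake is whether the fifth objective is answered for both groups.

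**Working it through.** **Inputs**
- Patients interviewed: 15-25 (synopsis, "Patient Semi-Structured Interview 15-25").
- Clinicians interviewed: 10-15 (synopsis, "Clinician Semi-Structured interview 10-15").
- Response: about 50%, one rate for both groups (section 7.1).
- Target: 15-25 combined (section 7.1).

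**1. Does the stated target follow from its stated basis?**

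Pool = patients + clinicians: 15 + 10 = 25 to 25 + 15 = 40.

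Expected replies = 0.5 × pool: 0.5 × 25 = 12.5 to 0.5 × 40 = 20.

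The stated 15-25 is not reproduced. It would need 15/25 = 60% to 25/40 = 62.5%.

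**2. Would the count be reached?** Taking replies as binomial at 50%:

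| Invited | Chance of at least 15 replies | Chance of at least 25 replies |
|---|---|---|
| 25 | 0.21 | below 0.001 |
| 40 | 0.96 | 0.08 |

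So the rule behaves very differently depending on which end of the range is meant. At 15 with a large pool it would usually cut collection short. At 25, or at 15 with the smallest pool, it would usually not be met, leaving the sub-study with no defined end.

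**3. How few patients could satisfy the target?**

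Fewest patients = max(0, target − clinicians interviewed).

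| Target | 10 clinicians interviewed | 15 clinicians interviewed |
|---|---|---|
| 15 | 5 | 0 |
| 25 | 15 | 10 |

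These are floors that need every clinician to reply. At 50% response the chance of that is 0.5^10 ≈ 0.001 with 10 clinicians and 0.5^15 ≈ 0.00003 with 15.

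**4. What does 50% in each group give?**

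Patients: 0.5 × 15 = 7.5 to 0.5 × 25 = 12.5, about 8-13.

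Clinicians: 0.5 × 10 = 5 to 0.5 × 15 = 7.5, about 5-8.

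Patients would then be 7.5/12.5 = 60% to 12.5/20 = 62.5% of replies.

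**5. How far could the response mix move a pooled figure?** All rates in this step are assumptions, for illustration only. Take 25 patients and 15 clinicians, with 30% of patients and 80% of clinicians reporting a change.
- 50% response in both: (0.3 × 12.5 + 0.8 × 7.5)/20 = 48.8%.
- 30% response in patients, 80% in clinicians: 7.5 + 12 = 19.5 replies, and (0.3 × 7.5 + 0.8 × 12)/19.5 = 60.8%.

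The pooled figure moves 12 points with nobody's opinion different. The movement equals the gap between the groups times the change in patient share, here 50 points × (0.625 − 0.385). With a gap of 10 points it would be about 2.4 points, and with no gap it would be nil.

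**The case against.** The strongest reply is that the protocol combines a headcount, not an analysis. A reader might infer that a single merged estimate is planned for the fifth secondary objective. The documents do not support that: section 7.2 names no pooled summary, the primary objective is also worded for patients and clinicians jointly without implying one number, and reporting by group may be settled in an analysis plan that is not shown. This stands, so the dependence on response mix is conditional on someone pooling.

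A reader might also infer that the sub-study is likely to finish with almost no patients. That is not supported either. The extreme case needs every clinician to reply before the patients do; at equal response patients are the majority. The illustration in step 5 itself yields 7-8 patients, and it arises from non-response, not from early stopping.

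The end rule does not name the sub-study, and a range does not fix a stopping number; 15-25 may have been meant as an expected yield. That is a fair reading of the intention, but the instrument is a questionnaire and no other end rule applies to it, so the text should say so. Inviting the former interviewees is already planned and is not a gap. Finally, in a closed pool a target per group cannot create replies. That is true, and it is why the remedy is a closing date and expected numbers, not quotas.

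**Conclusion.** The point holds in a limited form. The protocol sets a combined target with no minimum per group, has an end rule that appears to cover the sub-study without fixing its number, and gives a target that its own 50% does not produce (12.5-20 against 15-25). Applied at 15, the rule would discard available replies and favour the faster group; the floor of 0-5 patients is a boundary case that requires strongly unequal response. The documents do not show that a pooled result is planned or that patients will be nearly absent.

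The conclusion rests on reading the questionnaire end rule as covering this e-questionnaire and on the interview numbers being as planned. The binomial figures assume independent replies at 50%. Severity is minor: the sub-study is descriptive and unpowered, and serves one of five secondary objectives.

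**What to change.** - In the End of Study Definition, exempt the Covid-19 sub-study from stopping on a count and close it on a fixed date after all former interviewees have been invited.
- In section 7.1 and the synopsis, replace the combined target with expected replies per group at the stated 50%: about 8-13 patients and 5-8 clinicians, 12.5-20 in total before rounding. State that this corrects 15-25. If the actual interview numbers are known, use half of those.
- State that patients and clinicians are reported separately for the fifth secondary objective, each with the number invited and the response rate.

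The cost is a few lines of wording and no extra participants. The downside is that each group's result is visibly small and the stated total is slightly lower.

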7.2. Method of analysis

Quantitative Analysis

Descriptive statistics will be predominantly used to analyse the quantitative sections of the questionnaires. However, if no clear trends are identified then further statistical analysis is likely to include the following:

- One sample t-tests will be used for Likert scales to compare the mean of scores with the central value of the score
- Chi-square or Fisher’s exact test to assess the associations between patient groups stratified according to demographic parameters
- Comparison of quantitative variables, two sample t-tests and nonparametric Mann-Whitney tests will be applied
- Multivariate analysis by binary logistic regression to examine the variables influencing the willingness to use technology.

Qualitative Analysis

Interviews will be transcribed and analysed using thematic analysis, with the assistance of coding software. This involves first reading and re-reading the transcripts to gain familiarity with the data; iterated coding leading to the

generation of overarching themes from patterns emerging from the data; reflection on and definition of the themes and how they contribute to an understanding of the data; and finally the writing of a thick description of the data. Free-text questions from questionnaires will be analysed in the same manner. To increase reliability coding will be done by both a clinician and computer scientist who will monitor and discuss themes emerging throughout the process.

8. Ethics

This study will be carried out in accordance with the ethical principles in the Research Governance Framework for Health and Social Care, Second Edition, 2005 and its subsequent amendments as applicable, and applicable legal and regulatory requirements.

Summary of Main Issues

- Confidentiality and Data Storage:

Data will be stored in compliance with Data Protection Act. All data will be pseudo-anonymised where data of birth and initials will be linked to a unique participant identifier for the patient in an encoded fashion.

- Interview Transcription:

Interviews will be audio-recorded and transcribed by an external company (Bristol Transcription Services). Participants' identity will be confirmed at the start of interview, prior to commencement of audio-recording. Once audio-recording has commenced only the participants' unique study number will be used. The audio recording will be deleted once transcription is complete. Transcripts will be labelled with the participant's unique study number and no other patient identifiable information will be included. Transcripts will be analysed and coded at EECS. Once analysis is complete the transcripts will be stored within a secure locked room within the Department of Experimental Medicine and Rheumatology.

- Inclusion/Exclusion:

Correct adherence to study inclusion/exclusion criteria will be observed, following appropriate recruitment, screening and consent methods.

- Consent:

A member of the study team will discuss the study with patients and answer any questions the patient may have. Once the patient has read the Participant Information Sheet, and have had time to consider whether they wish to

participate, consent will be taken. For the Covid-19 sub-study, the completion of the questionnaire will be considered as sufficient consent to participate.

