
Statistical methodology and analysis (if applicable)
	
Due to the study type there is no statistical powering for the patient population.
 
Information from the interview studies and any open text boxes in questionnaires will be analysed using thematic analysis to code emerging themes from patient and clinician interviews and 'free text' questionnaire answers.
 
Descriptive statistics will be predominantly used to analyse the quantitative sections of the questionnaires. However, if no clear trends are identified then further statistical analysis will proceed with support of the Experimental Medicine and Rheumatology Statistician, and is likely to include the following:
 
 ● One sample t-tests will be used for Likert scales to compare the mean of scores with the central value of the score ● Chi-square or fisher's exact test to assess the associations between patient groups stratified according to demographic parameters ● Comparison of quantitative variables, two sample t-tests and nonparametric mann-whitney tests will be applied ● Multivariate analysis by binary logistic regression to examine the variables influencing the willingness to use technology.

Study duration
	
Recruitment & interviews: 18 months Analysis: 12 months

3. Introduction

PAMBAYESIAN is an EPSRC funded project that aims to develop intelligent technological support for those with chronic conditions. One strand of this project is to understand patient and clinician needs within the context of routine clinical care. This group of studies forms one strand of that work and focuses on rheumatoid arthritis: one of the PAMBAYESIAN case study areas.

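### Questionnaire comparisons are made conditional on seeing no clear trend, so the data decide whether secondary objectives 1, 3 and 4 are tested

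*Protocol*

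**What the plan says.** Section 7.2 of the protocol opens its quantitative part with the default: "Descriptive statistics will be predominantly used to analyse the quantitative sections of the questionnaires". It then continues: "if no clear trends are identified then further statistical analysis is likely to include the following". Four items follow: one-sample t-tests on Likert scores, chi-square or Fisher tests, two-sample t-tests with Mann-Whitney tests, and binary logistic regression. All four sit behind that condition.

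The synopsis, under its statistical methodology entry, has the same rule: "if no clear trends are identified then further statistical analysis will proceed with support of the Experimental Medicine and Rheumatology Statistician". It is therefore not a slip in one section.

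Section 4.2 sets the questions that these methods would have to answer:

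- Objective 1: "Do the perceived opportunities and challenges vary according to patient demographics e.g. disease activity, disease duration, patient age"
- Objective 3: "Do the perceived opportunities and challenges vary according to clinician demographics e.g. age, subspeciality"
- Objective 4: "Are there significant differences in patient and clinician expectations for health technology assessed parameters"

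Neither section defines a clear trend, says who judges it, or says whether it is judged item by item or for a questionnaire as a whole.

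**The concern.** Objectives 1, 3 and 4 are comparisons between groups. Each needs an estimate of the difference and its uncertainty whatever the raw percentages look like. As written, the plan makes that step depend on the results, and in the wrong direction: formal analysis is foreseen when nothing stands out, and none is foreseen when something does. A visible difference between patients and clinicians is exactly when objective 4's question about significance most needs an answer.

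Two things are at stake. First, with targets of 100 patients and 40 clinicians, apparent differences between subgroups can easily arise by chance, and the plan would let them be reported without any measure of uncertainty. Second, if the condition is applied item by item, real differences large enough to be seen are the ones least likely to be tested.

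**Working it through.** The protocol states no alpha, power, SD or effect size for the questionnaires, so it has no figure to reproduce. What follows is an illustration.

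**Inputs from the protocol (section 7.1):** 100 patient and 40 clinician questionnaires.

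**Assumptions, not in the protocol:**
- Two-sided alpha of 0.05 and a normal approximation.
- Equal splits within patients (50 v 50) and within clinicians (20 v 20), and 100 v 40 for patients against clinicians.
- Differences in SD units.
- The condition is applied to each comparison: a test is run only if the observed difference is smaller in absolute value than a cut-off c, with c = 0.3, 0.5 or 0.8 SD.

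**Step 1. Smallest observed difference that reaches p < 0.05.** SE = √(1/n₁ + 1/n₂); critical difference = 1.96 × SE.
- 50 v 50: SE = √(1/50 + 1/50) = 0.200; critical = 0.39 SD
- 20 v 20: SE = √(1/20 + 1/20) = 0.316; critical = 0.62 SD
- 100 v 40: SE = √(1/100 + 1/40) = 0.187; critical = 0.37 SD

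If c lies below these values, as 0.3 SD does for all three, every test that is run must be non-significant.

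**Step 2. Chance that a test is run and significant when the true difference is 0.5 SD.** Without the condition this is 1 − Φ((critical − 0.5)/SE). With it, for c above the critical value, it is Φ((c − 0.5)/SE) − Φ((critical − 0.5)/SE); the opposite tail is negligible. Example for 50 v 50 and c = 0.5: Φ(0) − Φ((0.392 − 0.5)/0.200) = 0.500 − 0.295 = 0.205.

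| Comparison | No condition | c = 0.3 SD | c = 0.5 SD | c = 0.8 SD |
|---|---|---|---|---|
| 50 v 50 patients | 71% | 0% | 21% | 64% |
| 20 v 20 clinicians | 35% | 0% | 0% | 18% |
| 100 patients v 40 clinicians | 76% | 0% | 26% | 71% |

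At c = 0.5 SD the test is run only about half the time in each row.

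**Step 3. Chance that a difference looks clear when there is none.** With a true difference of zero, this is one minus the probability that the test is run.
- c = 0.3 SD: 1 − 0.866 = 13% (50 v 50); 1 − 0.657 = 34% (20 v 20); 1 − 0.891 = 11% (100 v 40)
- c = 0.5 SD: 1 − 0.988 = 1%; 1 − 0.886 = 11%; 1 − 0.992 = 1%

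These are the chance findings that would be described with no test or interval foreseen.

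**Step 4. Type I error.** With a true difference of zero and c = 0.5 SD, run-and-significant occurs in 3.8%, 0% and 4.2% of cases. The condition lowers the rate of false significant results below 5%; it does not raise it.

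**The case against.** The strongest reply is about weight. The study is openly unpowered, mostly qualitative and non-interventional. Its primary endpoint (section 4.3) is thematic analysis, which the condition does not touch. Mainly descriptive reporting of 100 and 40 questionnaires is legitimate, and no confirmatory decision rests on these tests. That stands, and it limits the severity.

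The second reply is about wording. A reader might infer that testing is forbidden once a trend is seen. The text does not say so: description is only the predominant approach, the list is only likely, and descriptive results can carry intervals. The fair statement is that the plan provides for no test or interval in that case. A reader might also take it as settled that testing is aimed at the flattest items. That follows only if the condition is judged item by item. If it is judged for a whole questionnaire, the choice is all or nothing, and only the dependence on the data remains.

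The third reply is that section 7 promises statistician support in planning the quantitative analysis, and that an analysis plan not shown may settle details. This does not answer the point. Section 7 does not lift the condition, and the synopsis places the statistician's support after the same condition. The protocol does not leave the matter open for a later document; it states a rule, and the rule is the problem.

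**Conclusion.** The rule is wrong as written and should be fixed, but it concerns secondary, exploratory objectives only. On either reading of the condition, the observed results decide whether the comparisons for objectives 1, 3 and 4 are made.

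The size of the loss cannot be fixed from the protocol because the cut-off is undefined. Under the stated assumptions it runs from total (0.3 SD) through severe (0.5 SD) to small for the patient and patient-clinician comparisons at 0.8 SD, where the clinician comparison still loses about half of its chance of a significant result. These figures apply to a condition judged comparison by comparison, with equal splits; they are not estimates of what this study will show.

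A reader might infer that the reported p-values would be too liberal or that the study's main conclusion is compromised. Neither follows: the type I error of a single test is not inflated, and the thematic endpoint does not depend on these analyses.

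**What to change.** In section 7.2 and in the synopsis, delete the clause that makes further analysis depend on the absence of clear trends. Replace it with a statement that the comparisons for secondary objectives 1, 3 and 4 are run whatever the descriptive results show, reported as estimated differences with 95% confidence intervals, with any p-values labelled exploratory.

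When rewording, name the groups for each objective. The chi-square and Fisher line at present covers only patients ("exact test to assess the associations between patient groups stratified according to demographic parameters"), so the clinician comparison in objective 3 is not named there.

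The cost is a few sentences of protocol wording and a little more analysis, with no new data. The downside is a larger number of exploratory p-values, which the label and the emphasis on intervals should keep in proportion.
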